### **2.2 Study Outcome**

#### **2.2.1 Primary outcome**

The primary outcome of this study is the precision of the lung nodule localization, which was specified by the localizer deviation. As the center of the nodule is the designed target, localizer deviation is measured between the center of nodule and the localizer. Regarding to measurement of the localizer deviation, because the localizer and the target nodule might be not on the same section of the CT scan, it is impossible to accurately measure the deviation from two-dimensional images.

Therefor we reconstruct the CT images upon nodule localization into three-dimensional virtual model, and precisely measure the localizer deviation in three dimensions.

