#### **3.2 Sample Size Calculation**

The study was designed to confirm the non-inferiority of template-guided lung nodule localization compared to CT-guided lung nodule localization in terms of localization accuracy. And the accuracy of lung nodule localization was quantified by the localizer deviation between the localization and the center of the target nodule.

The expected difference of localizer deviation between CT- and template-guided group was 3.5mm according to priori study. Deviation of 5mm is set as non-inferiority margin. We needed to randomize 140 patients (70 each group) to give 90% power with one-sided alpha of 0.05. To allow for some dropouts, inclusion of 100 patients per group is planned.

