### **3.5 Statistical Analysis**

To decide whether the localization accuracy, radiation exposure and complication rate in the two groups are significantly different, three tests are used: 1) independent samples  $t$  tests for continuous variables that were normally distributed; 2)  $X^2$  tests for categorical variables, and 3.) Mann-Whitney U test for continuous variables that were not normally distributed.

Because of the possibility of patients withdraw, intention-to-treatment (ITT) analysis and efficacy analysis are both performed. ITT analysis is conducted for participants who received lung nodule localization and subsequent surgery. Efficacy analysis is only performed for patients who received lung nodule localization according to their assignment. All statistical analyses are two-tailed with a significance level of 0.05.

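### An undefined normality check decides whether the primary outcome is compared by means or by ranks, and the rank branch gives no millimetre difference to set against the 5 mm margin

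*Combined protocol and SAP*

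**What the plan says.** Section 2.2.1 defines the primary outcome as a distance: "localizer deviation is measured between the center of nodule and the localizer", taken in three dimensions from the reconstructed CT images.

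Section 3.2 sets up a non-inferiority comparison of that distance: "Deviation of 5mm is set as non-inferiority margin". It does not say whether the 5 mm applies to means, medians or a location shift.

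Section 3.5 governs the analysis: "To decide whether the localization accuracy, radiation exposure and complication rate in the two groups are significantly different, three tests are used". For a continuous outcome the choice is between independent-samples t "tests for continuous variables that were normally distributed" and the "Mann-Whitney U test for continuous variables that were not normally distributed". The primary outcome has no rule of its own. The section gives no criterion for normality, no effect estimate and no confidence interval, and it does not mention the margin.

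Section 1.3.1 reports the earlier template result as a median of 10.0 mm, without an SD or interquartile range.

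**The concern.** The two branches answer different questions. The t test compares mean deviations. The Mann-Whitney test asks whether a deviation from one arm tends to exceed one from the other, and its p-value is not a quantity in mm. Which question the trial answers would be settled after the data are seen, by a check that nobody has defined.

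The rank branch is a realistic prospect. A distance is bounded at zero and often right-skewed, and the feasibility result was summarised by a median. If that branch is taken, the plan offers nothing to hold against 5 mm.

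Adding the margin to the existing tests, by subtracting 5 mm from the template arm before ranking, leaves part of the problem. A rank test shifted in this way matches a test of a 5 mm mean difference when the arms differ by a pure shift, but not in general. If deviations spread out as they grow, a 5 mm excess in the mean can look smaller than 5 mm on the rank scale, and non-inferiority could be declared too easily.

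**Working it through.** **1. The plan's own figure.** Section 3.2 states: "We needed to randomize 140 patients (70 each group) to give 90% power with one-sided alpha of 0.05". With the usual formula for means,

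n per group = 2(z₀.₉₅ + z₀.₉₀)² SD² / (5 − d)², where d is the true difference, template minus CT.

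No SD is given, so 70 cannot be reproduced. Solving for the SD:

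SD = (5 − d) × √(70 / (2 × 2.927²)) = (5 − d) × 2.021.

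The 3.5 mm expected difference is given without a direction or a summary measure:

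- template 3.5 mm worse: 1.5 × 2.021 = 3.03 mm
- no difference: 5 × 2.021 = 10.1 mm
- template 3.5 mm better: 8.5 × 2.021 = 17.2 mm

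The documents therefore fix neither the spread nor the shape. Every error rate below rests on an assumed distribution.

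**2. Where the rank test and the mean margin part.** Let T and C be template and CT deviations with E(T) − E(C) = 5, the edge of non-inferiority on the mean scale. A Mann-Whitney test on T − 5 against C has the correct level when T − 5 and C have the same distribution, so that P(T − 5 < C) = 1/2. If this probability exceeds 1/2, the test leans towards non-inferiority.

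Take assumed means of 6.5 and 11.5 mm. For 3D-normal error (Maxwell distance) the coefficient of variation is √(3π/8 − 1) = 0.422, so the SDs are 2.74 and 4.85 mm. For 2D-normal error (Rayleigh) it is √(4/π − 1) = 0.523, so the SDs are 3.40 and 6.01 mm. Evaluating ∫F_T(c + 5) f_C(c) dc numerically gives P(T − 5 < C) ≈ 0.519 and 0.526.

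At 70 per arm the null standard error is √(141 / (12 × 70 × 70)) = 0.049. The approximate one-sided error at nominal 0.05 is then:

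- Maxwell: 1 − Φ(1.645 − 0.019/0.049) = 1 − Φ(1.26) ≈ 0.10
- Rayleigh: 1 − Φ(1.645 − 0.026/0.049) = 1 − Φ(1.11) ≈ 0.13

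**3. Simulation.** True mean difference 5 mm, 70 or 100 per arm, one-sided 0.05, 3,000 to 20,000 trials per setting. The gated rule uses the shifted Mann-Whitney if Shapiro-Wilk is below 0.05 in either arm, and otherwise the t test against 5 mm. Entries are rates of false non-inferiority on the mean scale; a dash means no figure for that setting.

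| Assumed setting | Shifted Mann-Whitney | Gated rule | Welch against 5 mm |
|---|---|---|---|
| Pure 5 mm shift | about 5% | – | about 5% |
| Maxwell, 6.5 v 11.5 mm | 10–13% | 9–12% | 5–6% |
| Rayleigh, 6.5 v 11.5 mm | 13–18% | 14–18% | 5–6% |
| Maxwell or Rayleigh, 10 v 15 mm | – | 8–12% | 5–6% |
| 6.5 v 11.5 mm, final deviation capped at 20 mm | 3–6% | 3–6% | 4–6% |
| 5 v 10 mm, capped at 20 mm | 8–10% | 7–9% | – |
| Skewed, equal SD 4–8 mm | 3–12%, mostly at or below 5% | – | 4–5% |
| Gamma or lognormal, spread proportional to mean, CV 0.4–0.8 | 12–64% | – | 5–7% |

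In the uncapped settings at 6.5 v 11.5 mm, the rank branch was taken in 53–72% of Maxwell trials and 82–96% of Rayleigh trials.

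**4. Reading.** The rank route ranges from about nominal to far above it, according to a shape that the documents do not report. Across all these settings the Welch comparison stays between 4% and 7%.

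**The case against.** The strongest reply is that the test with these error rates is not in the plan. Section 3.5 tests for a difference and never uses the margin. At a true 5 mm excess, the Mann-Whitney test as written was significant in 99.97–100% of simulated trials, so it would flag the template arm as different. This stands: leaving the margin out of 3.5 is the larger flaw, and it is separate. The present point matters because anyone repairing that omission by adding 5 mm to the listed tests would keep the data-driven choice.

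A reader might infer that the plan would declare non-inferiority two to three times too often. The documents do not support that, for three reasons:

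- They give no SD or shape. The means of 6.5 and 11.5 mm are assumptions, and under a pure shift there is no inflation.
- Sections 5.1 and 5.2 apply a 2 cm accuracy threshold. If it in effect caps the final deviation, the inflation disappears at 6.5 v 11.5 mm and stays below twice nominal at 5 v 10 mm. The cap is itself an assumption: in the template arm the threshold applies to the scan before insertion, so the final deviation could exceed it.
- The margin's scale is unstated. Against a median or a location shift, calling these rejections false is partly circular. Even so, lognormal data with a true median difference of 5 mm gave 9–14% without a cap.

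It is also fair to say that a Hodges-Lehmann interval gives a shift in mm. It is a valid alternative if the margin is defined as a shift, but it estimates a mean difference only under conditions such as a pure shift.

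**Conclusion.** The point holds as a defect of specification. For the primary outcome, an undefined check on the trial data selects between two different quantities, and one of the branches cannot be compared with the 5 mm margin. That follows from sections 2.2.1, 3.2 and 3.5 alone. How likely the rank branch is remains a judgement, since the shape of the data is not reported.

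No single inflation factor can be attached. If the margin were built into the rank test, its error against a 5 mm mean difference would be about nominal under a pure shift or with deviations of 6.5 v 11.5 mm capped near 20 mm. It would be roughly 2 to 3 times nominal under assumed uncapped 3D- or 2D-normal error, and higher still for gamma or lognormal data whose spread is proportional to the mean. These figures assume one-sided 0.05, as in 3.2, and a margin on the mean scale.

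The case for change rests on the dependence on an unknown distribution, while a Welch limit stays near nominal in every setting tried.

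**What to change.** In section 3.5, state that:

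- localizer deviation is always analysed as the difference in means, template minus CT, with a Welch confidence interval, whatever a normality check shows;
- the 5 mm margin refers to this mean difference, and non-inferiority is concluded only if the upper confidence limit is below 5 mm;
- a bootstrap interval and a rank-based result (Mann-Whitney with the Hodges-Lehmann shift) are supportive only;
- the Mann-Whitney option remains for procedural length and DLP.

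The interval's level has to be given as well, because 3.2 plans a one-sided 0.05 and 3.5 a two-tailed 0.05. With the former the limit comes from a two-sided 90% interval, with the latter from a 95% interval.

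The cost is a sentence or two, with no change to data collection or sample size. The downside is that a few large deviations weigh more in a mean than in ranks. The supportive analyses would show whether the conclusion hangs on them.

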## **2 OBJECTIVES**

### **2.1 Study Objectives**

To evaluate the safety and accuracy of navigational template-guided method in percutaneous lung nodule localization.

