### **2.2.2 Secondary outcome**

The secondary outcome includes procedural length, radiation exposure dosage and related complication rate.

In order to facilitate the process of data collection, the procedural length of nodule localization was inferred from CT scanning parameter. The time length of nodule localization is calculated from patients receiving the initial CT scan to patients receiving the last CT scan for complication evaluation. And, the radiation exposure dosage (dose-length-product) is directly collected from monitor screen after the last CT scanning. The complication related to percutaneous lung nodule localization mainly includes pneumothorax, pulmonary hemorrhage and hemoptysis during the time of waiting for surgery. The occurrence of pneumothorax and pulmonary hemorrhage is evaluated by CT scanning immediately after localizer release.

Additionally, localizer dislodgement rate and the margin distance reported on frozen analysis are also compared between patients undergoing CT-guided nodule localization and patients receiving template-guided nodule localization.

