#### **4.6 Reasons for Withdrawal after Randomization**

When patients are firstly approached by research assistants, they are informed that they have the right to withdraw their consent to participate at any stage of the trial without influence on their medical care. Therefore, patients with intended withdrawal after randomization is excluded from the study.

As the decision of lung nodule localization need to be made at more than one day before the scheduled surgery to allow for template production, there is the possibility of premature randomization, which is that the assigned patient might not suitable for lung resection after preoperative assessment. Patient whose scheduled lung resection is cancelled is withdrawn from the analysis.

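### The set called ITT requires surgery after localization, so a localization complication that stops the resection drops out of the ITT complication comparison

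*Combined protocol and SAP*

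**What the plan says.** Section 2.1 gives the objective as "To evaluate the safety and accuracy of navigational template-guided method in percutaneous lung nodule localization". Section 2.2.2 makes complications a secondary outcome: "The secondary outcome includes procedural length, radiation exposure dosage and related complication rate". It also fixes when the main ones are read: "The occurrence of pneumothorax and pulmonary hemorrhage is evaluated by CT scanning immediately after localizer release". Under 2.2.2, 5.2 and 6.4.2, hemoptysis and other events are recorded while the patient waits for surgery.

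Section 3.5 defines two sets and gives withdrawal as the reason for having both: "Because of the possibility of patients withdraw, intention-to-treatment (ITT) analysis and efficacy analysis are both performed". The first: "ITT analysis is conducted for participants who received lung nodule localization and subsequent surgery". The second: "Efficacy analysis is only performed for patients who received lung nodule localization according to their assignment". No separate safety set is defined.

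Section 4.6 adds: "Patient whose scheduled lung resection is cancelled is withdrawn from the analysis". That sentence closes a paragraph on premature randomization, where the worry is that "the assigned patient might not suitable for lung resection after preoperative assessment".

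**The concern.** Membership of the ITT set depends on an event after randomization that the outcome itself can prevent. Pneumothorax, hemorrhage and waiting-period hemoptysis are all known before the operation, yet they count in the ITT comparison only if the operation goes ahead. A complication serious enough to stop it removes the patient, the event and any deviation already measured.

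The removal can only lower the affected arm's complication rate, and it falls on the worst events. If such events are more frequent in one arm, the comparison is tilted in favour of that arm. Section 4.3 says that there is no masking, so a decision to cancel may be made with the arm known, and equal loss in the two arms cannot be taken for granted.

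**Working it through.** **Step 1: who is in which set.** This applies the wording of 3.5, 4.6 and the conversion rule in 5.2 (a template patient whose pre-evaluated deviation exceeds 2 cm receives conventional CT guidance).

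| Patient | ITT set (3.5) | Efficacy set (3.5) |
|---|---|---|
| Localized as assigned, surgery done | in | in |
| Localized as assigned, complication stops surgery | out | in on the wording of 3.5; out if 4.6 covers every analysis |
| Template patient converted to CT guidance, surgery done | in | out |
| Template patient converted to CT guidance, complication stops surgery | out | out, however 4.6 is read |
| Attempt abandoned because of a complication, no surgery | out | out or unclear, since localization must have been received |

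The second row is the main case. The fourth can arise only in the template arm, because only that arm has a conversion rule. It takes the ordinary reading that a converted patient was not localized as assigned. No set covers all patients with an attempted localization, by assigned arm.

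**Step 2: which outcomes need surgery.** Deviation, procedural length, dose, CT-detected pneumothorax and hemorrhage, and waiting-period hemoptysis do not. Dislodgement, margin distance, successful wedge resection (6.4.3) and postoperative complications over one month (3.4) do.

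**Step 3: size, by illustration only.** The plan has no figure to reproduce here: it states neither a complication rate nor a cancellation rate. Only n = 100 per arm comes from the plan (3.2); x and k below are assumptions. If x of n patients have a complication and k of those x lose their surgery, the reported rate is (x − k)/(n − k).

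| Assumed true rate | k = 1 | k = 2 | k = 3 | k = 5 |
|---|---|---|---|---|
| 10% | 9/99 = 9.1% | 8/98 = 8.2% | 7/97 = 7.2% | 5/95 = 5.3% |
| 20% | 19/99 = 19.2% | 18/98 = 18.4% | 17/97 = 17.5% | 15/95 = 15.8% |
| 30% | 29/99 = 29.3% | 28/98 = 28.6% | 27/97 = 27.8% | 25/95 = 26.3% |

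Each lost patient lowers the arm's rate by about 0.7 to 1.0 percentage point. The subgroup of surgery-stopping complications is affected far more: 1 to 5 such events per 100 appear in the ITT set as 0/99 to 0/95.

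**Step 4: effect on the comparison, again with assumed counts.**

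- Equal true rates of 20/100, with 4 lost in the template arm and 1 in the control arm: 16/96 = 16.7% against 19/99 = 19.2%, an apparent template advantage of 2.5 points where none exists. This would not be significant (uncorrected chi-square p about 0.65).
- True rates of 10/100 and 20/100, p = 0.048. Losing 2 events from the higher arm gives 10/100 against 18/98 and p = 0.091. Losing 5 gives 10/100 against 15/95 and p = 0.227. A real difference in harm can be blurred by a few losses.

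**The case against.** The case on the other side has four parts.

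1. *The efficacy set does not require surgery.* On the wording of 3.5, a patient localized as assigned stays in it with the complication, even if the resection is then cancelled. This stands. A reader might infer that such a patient vanishes from every analysis, so that surgery-stopping complications count as zero by construction. The documents support that for the ITT set only. The efficacy set narrows the gap but does not close it: it omits converted template patients and may omit abandoned attempts.

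2. *Section 4.6 concerns premature randomization.* Its natural setting is a cancellation before localization. This is fair, and 4.6 should be called ambiguous rather than read as a rule that deletes complications. The ITT problem does not depend on it, since the condition in 3.5 is enough.

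3. *Such cancellations may be rare or absent.* Section 1.3.1 expects most complications to be minor and reports no severe ones with the template in the feasibility trial. No section describes a complication cancelling surgery, and the counts in the illustration are invented. This also stands, and it is why no size can be claimed.

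4. *Safety is still watched.* Events are recorded on site and while waiting (6, 6.4.1, 6.4.2), the data monitoring committee sees all data (3.3), and adverse events are reviewed (8). A reader might infer that the trial cannot answer its safety objective. The documents do not support that: complications that do not stop surgery remain in the ITT comparison, and the recorded data would allow a count over all localized patients. What monitoring does not do is put the lost events back into the planned comparison.

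**Conclusion.** The concern holds in limited form. The ITT set in 3.5 can omit localization complications that stop the resection, and 4.6 leaves open whether they are omitted everywhere. Converted template patients whose surgery is then stopped are in neither set. For the affected arm the bias is always towards a lower complication rate, and it falls on the most serious events.

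Its size cannot be derived from the documents. It is zero if no resection is cancelled after localization. At assumed true rates of 10% to 30% and 100 patients per arm, it is about 0.7 to 1.0 percentage point per lost patient. It bears mainly on a secondary outcome, although that outcome answers the safety half of the objective; deviations measured in these patients also leave the ITT analysis. This should be fixed because the remedy is cheap, but it does not undermine the trial.

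**What to change.** In 3.5:

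- Analyse localization-related complications, procedural length and dose in all randomized patients in whom localization was started, by assigned arm, whether or not surgery followed.
- Analyse deviation in the same set where a localizer was placed and measured. An abandoned attempt may have no deviation and no CT after release, so report abandoned attempts by arm.
- Keep the surgery condition only for dislodgement, margin distance, successful wedge resection and postoperative complications. Report postoperative complications separately from localization-related ones.

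In 4.6, limit the cancellation rule to cancellations before localization starts, and report later cancellations by arm with the reason.

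The cost is wording in two sections. Localization events are already recorded on site and during the wait for surgery, so no extra patients or procedures are needed. The only addition is a short table of abandoned attempts and late cancellations by arm.

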### **5.1 Control Group**

Patients in the CT-guided group received conventional CT-guided percutaneous lung nodule localization using a hookwire system. After patients were positioned on the examining table of the CT scanner (patient's position was decided based on the location of the target nodule), the initial CT scan was conducted through the area of interest using a slice thickness of 3 mm. The localizer insertion site was determined by the CT gantry laser lights and a metal marker on the skin. The insertion length and angle were measured on CT images, and the localizer was then inserted without penetrating the pleura. Afterwards, repeated CT scans were taken to confirm or redirect the localizer in order to obtain adequate accuracy of nodule localization. Based on previous experience, deviations of  $\leq 2$  cm between the localizer and the center of the target nodule were considered accurate enough to allow for safe nodule localization. After confirmation of accurate localizer placement, the practitioner inserted the localizer into

the lung parenchyma and removed the cannula of hookwire.

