## **5.2 Experiment Group**

Patients in the template-guided group underwent template-guided percutaneous lung nodule localization using a hookwire. After template placement and prior to hookwire insertion, an initial CT scan is obtained to pre-evaluate the accuracy of nodule localization. If the deviation is less than 2 cm on the initial CT scan, the hookwire is inserted, and the localizer is deployed. However, if the deviation  $>2$  cm based on the pre-evaluation on the initial CT scan, patients would receive conventional CT-guided localization.

After successful nodule localization, the CT scan is immediately obtained in order to evaluate the incidence and severity of the pneumothorax and hemorrhage in both groups. Afterwards, patients are wheeled back to the unit where they wait for the scheduled surgery. During the waiting period, patients are closely observed by nurses, and any occurrence of dyspnea and hemoptysis are detailly recorded.

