## **6.1 Measurement of Localization Accuracy**

The accuracy of nodule localization was defined by the deviation between the localizer and the center of the target nodule on CT images. Because the target nodule and localizer are in the three-dimensional space of a patient's thoracic cage, which may not be seen on the same cut of CT scan, it is difficult to precisely measure the deviation directly on the 2D images of CT scan. In order to accurately measure the deviation, computer-aided design (CAD) software is introduced to precisely measure the deviation.

Firstly, patient's thorax is reconstructed based on CT images upon nodule localization. Then the deviation is mathematically calculated using the CAD software.

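### The efficacy set may drop converted patients from the template arm only, the 'ITT' set depends on later surgery, and neither set is named as deciding non-inferiority

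*Combined protocol and SAP*

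**What the plan says.** Section 3.5 plans two analysis sets: "intention-to-treatment (ITT) analysis and efficacy analysis are both performed". The first is described thus: "ITT analysis is conducted for participants who received lung nodule localization and subsequent surgery". The second: "Efficacy analysis is only performed for patients who received lung nodule localization according to their assignment". Neither is named as the one on which non-inferiority is judged.

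In the template arm, section 5.2 states: "After template placement and prior to hookwire insertion, an initial CT scan is obtained to pre-evaluate the accuracy of nodule localization". For a reading above 2 "cm based on the pre-evaluation on the initial CT scan, patients would receive conventional CT-guided localization". In the control arm, section 5.1 makes correction part of the method: "repeated CT scans were taken to confirm or redirect the localizer in order to obtain adequate accuracy of nodule localization".

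For the primary outcome, section 2.2.1 says that "localizer deviation is measured between the center of nodule and the localizer". Section 6.1 adds that the patient's "thorax is reconstructed based on CT images upon nodule localization". Section 4.6 excludes patients who withdraw consent after randomization and withdraws from the analysis those whose resection is cancelled. It does not mention conversion.

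**The concern.** In a non-inferiority trial the efficacy set is usually read as a check on the ITT result. If it leaves out the template patients with the worst pre-insertion readings and keeps every redirected control, agreement between the two sets gives little reassurance about the template itself.

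The set called ITT depends on something that happens after randomization and after the primary outcome is measured. Because no deciding set is named and conversion is not addressed, these choices can be made after the data are seen, in a trial without masking (section 4.3). A reader also cannot tell whether the result describes the template or the template with CT back-up.

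**Working it through.** **1. The two arms side by side.**

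| | Template arm | Control arm |
|---|---|---|
| Inadequate reading before final placement | Reading above 2 cm: converted to CT-guided localization (5.2) | Redirected within CT guidance (5.1) |
| Localized as assigned, plain reading of 3.5 | No | Yes |
| In the efficacy set | Removed | Kept |

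The selecting variable is a reading taken before hookwire insertion. The primary outcome is the three-dimensional distance on images taken upon localization (2.2.1, 6.1). They are successive readings of the same quantity, not the same measurement.

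**2. Can the plan's figures give a conversion rate?** Section 3.2 gives 70 per group, margin 5 mm, 90% power, one-sided alpha 0.05 and an expected difference of 3.5 mm, without an SD or a direction. So 70 per group cannot be reproduced. Solved backwards, SD = d × √35 / (1.645 + 1.282), where d is the distance from the true difference to the margin:
- 3.5 mm adverse to the template: d = 1.5, SD = 3.03 mm
- no true difference: d = 5, SD = 10.11 mm
- 3.5 mm in the template's favour: d = 8.5, SD = 17.18 mm

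Assume lognormal template readings with the 10.0 mm feasibility median (1.3.1). The share above 20 mm is then about 0.8%, 16% and 22%. The documents do not fix the conversion rate.

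**3. Direction.** Let p be the share converted, K the mean final deviation of unconverted template patients, B the mean final deviation of converted patients after CT guidance, H the mean they would have had with the template, and C the control mean. A larger difference is worse for the template.
- Efficacy set: K − C
- Template with CT back-up: (1 − p)K + pB − C
- Template alone: (1 − p)K + pH − C

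Efficacy set minus template alone = −p(H − K). This favours the template when H > K, that is, when the first reading predicts the final one. Efficacy set minus template with back-up = −p(B − K). This is adverse to the template when B < K. H is never observed, because section 5.2 converts these patients.

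**4. Illustration; the inputs are assumptions.** Both template readings are lognormal with median 10 mm and log-scale correlation r. The true template-alone difference is 5 mm, and converted patients perform like controls on average (B = C). With z the 1 − p normal quantile, σ = ln 2 / z and M = 10·exp(σ²/2):
- K = M·Φ(z − rσ)/(1 − p)
- efficacy difference = 5 − (M − K)
- back-up difference = (1 − p) × efficacy difference

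For p = 5% and r = 1: z = 1.645, σ = 0.421, M = 10.93, K = 10.93 × 0.8894 / 0.95 = 10.23. The efficacy difference is 5 − 0.70 = 4.30 mm, and the back-up difference is 0.95 × 4.30 = 4.09 mm.

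| p | r | Template alone | Efficacy set | Template with back-up |
|---|---|---|---|---|
| 1% | 1 | 5.00 | 4.88 | 4.83 |
| 5% | 1 | 5.00 | 4.30 | 4.09 |
| 5% | 0.7 | 5.00 | 4.56 | 4.33 |
| 5% | 0 | 5.00 | 5.00 | 4.75 |
| 10% | 1 | 5.00 | 3.34 | 3.00 |
| 10% | 0.7 | 5.00 | 3.93 | 3.54 |

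(mm; computed before rounding.) The efficacy set is at or below the template-alone difference and, under B = C, above the back-up difference. If converted patients are harder cases than the average control, the second gap narrows or reverses.

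**5. The ITT set.** Deviation is read on images taken upon localization (6.1). Pneumothorax and hemorrhage are read on the CT after localizer deployment (2.2.2, 6.4.1). All precede surgery, yet 3.5 requires surgery and 4.6 withdraws cancelled cases. A patient localized and then cancelled has these outcomes but is left out.

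**The case against.** A reader might infer that the efficacy set inflates the chance of a false non-inferiority claim. The documents do not support this as a general statement. In a simulation under the step 4 assumptions (70 per group, one-sided 0.05 Welch test against 5 mm, controls lognormal with the same σ and truncated at 20 mm), 5% conversion and identical readings give non-inferiority in about 35% of trials in the efficacy set. Scoring the template alone gives about 6%. But the set recommended below, with converted patients' final deviations, gives about 51%, because it estimates a smaller true difference. Such rates refer only to the template alone, a quantity that section 5.2 never lets be observed in converted patients. They are neither evidence for the recommended analysis nor evidence of bias against it. Section 3.5 also specifies no margin test.

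Other objections stand in part:
- Conversion is written into the experimental procedure, so converted patients may count as localized as assigned. Nobody is then removed, but the efficacy set is no check on conversion.
- The final deviation in the randomized arm is already the natural reading of 2.2.1, 6.1 and the label ITT. What is missing is an explicit sentence.
- Both analyses are planned, which limits later choice without removing it.
- Section 4.6 ties cancellation to preoperative assessment, so few patients may be localized and then cancelled. Surgery is needed for dislodgement and margin distance.

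It would also go too far to say that patients are removed on the primary outcome itself. They are removed on a pre-insertion reading.

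**Conclusion.** The point holds in a limited form and should be fixed. On the plain reading of 3.5 with 5.2, the efficacy set is selected in the template arm only, on an earlier reading of the outcome quantity. On the other reading there is no bias from this source. The set called ITT is not intention-to-treat for outcomes read before surgery, and no set is named to decide non-inferiority. These are matters of text and rest on no simulation.

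The size is unknown, and the effect of the surgery condition cannot be sized at all. The direction depends on the question: in favour of the template when the target is the template alone and the readings are correlated; not necessarily so, and possibly the reverse, when the target is template with CT back-up. The figures in step 4 show direction only. Confidence is medium.

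**What to change.** - **ITT set.** Define it as all randomized patients with an observed outcome, analysed as assigned. Remove the surgery condition for outcomes read before surgery, and align section 4.6. Report withdrawn, cancelled and never-localized patients by arm and reason.
- **Deciding analysis.** Keep converted patients in the template arm with their final deviation. State that this estimates template with CT back-up and does not show the accuracy of the template alone. Base the non-inferiority conclusion on this set.
- **Efficacy set.** State whether a converted patient counts as localized as assigned. If not, treat the set as supportive only.
- **Conversions.** Report the number converted.
- **Optional sensitivity analysis.** Score converted patients with the deviation from the pre-insertion scan already taken. Label it as a projected path, not like-for-like with controls measured after redirection.

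The 2 cm conversion rule is unchanged. The cost is wording, one count and, if the optional analysis is done, a few measurements on existing scans. The price is that the conclusion is limited to template with CT back-up.
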